**EFFECT OF VITAMIN D3 SUPPLEMENTATION ON HEPSIDIN AND FERRITIN SERUM
LEVELS IN CHILDREN WITH CHRONIC KIDNEY DISEASE**

May 1st 2023

EFFECT OF VITAMIN D3 SUPPLEMENTATION ON HEPSIDIN AND FERRITIN SERUM LEVELS IN CHILDREN WITH CHRONIC KIDNEY DISEASE

Protocol

Responsible Personnel

Principal Investigator Contact Information

Name: [name]

Title: MD

Institution: Department of Pediatrics, Faculty of Medicine, Hasanuddin University

Address: [name]

[contact]

Email: [contact]

Summary:

This study aim to assess the effect of Vitamin D administration on Hepcidin and Ferritin serum level in children with chronic kidney diseases. It is a clinical trial involving 43 chronic kidney disease patients at [name] Hospital in Makassar, Indonesia. Subjects are enrolled into two different groups, one with glomerulus filtration rate (GFR) more than 90 mL/min/1,73 m² and the other group consist of children with GFR less than 90 mL/min/1,73 m². Both group will be given the same dose of Vitamin D, which is 2000 IU for 6 weeks. Measurements of vitamin D, hepcidin and ferritin level will be before and after Vitamin D supplementation.

Introduction:

Chronic kidney disease (CKD) is a significant global health issue characterized by a gradual decline in kidney function over time. Defined by the Kidney Disease: Improving Global Outcomes (KDIGO) guidelines, CKD involves abnormalities in kidney structure or function lasting more than three months, which can lead to complications such as anemia. In children, CKD can adversely affect growth patterns and is closely linked to anemia due to reduced erythropoietin production, which disrupts iron homeostasis essential for oxygen transport in the body.

Anemia in CKD patients is primarily driven by iron deficiency, with studies indicating that the incidence ranges from 7.2 to 13.96 per 1,000 people annually, contributing to approximately 800,000 deaths globally. In pediatric populations, the prevalence of anemia among children with CKD is notably high, affecting 36-58% of patients in regions like the United States and Germany. The increasing incidence of CKD in children is likely related to longer life expectancy and improved treatment options, although data on early-stage CKD remain limited.

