Vitamin D deficiency is another critical issue associated with CKD, particularly in children. Research shows that a significant percentage of patients undergoing hemodialysis exhibit low vitamin D levels, which can exacerbate anemia by lowering hemoglobin levels. Vitamin D plays a vital role in erythropoiesis, and its deficiency correlates with increased serum hepcidin levels—a hormone that regulates iron metabolism and can hinder iron absorption and release from stores.

Given the interconnectedness of vitamin D levels, hepcidin concentration, and anemia in children with CKD, research is warranted to explore the effects of vitamin D supplementation on serum hepcidin and ferritin levels. There is currently a lack of studies addressing this relationship,

especially in Indonesia. This research aims to fill the gap in knowledge regarding vitamin D's potential benefits for managing anemia and iron homeostasis disorders in pediatric CKD patients.

Objectives of Trial:

1. **Primary Objective**
 - a. To assess the effect of Vitamin D supplementation on hepcidin and ferritin serum level in children with CKD
2. **Secondary Objective**
 - a. To assess vitamin D, hepcidin, and ferritin level in children with CKD and GFR less than 90 ml/min/1,73 m² before vitamin D3 supplementation
 - b. To assess vitamin D, hepcidin, and ferritin level in children with CKD and GFR more than 90 ml/min/1,73 m² before vitamin D3 supplementation
 - c. To assess vitamin D, hepcidin, and ferritin level in children with CKD and GFR less than 90 ml/min/1,73 m² after vitamin D3 supplementation
 - d. To assess vitamin D, hepcidin, and ferritin level in children with CKD and GFR more than 90 ml/min/1,73 m² after vitamin D3 supplementation
 - e. To compare vitamin D, hepcidin, and ferritin level in children with CKD and GFR less than 90 ml/min/1,73 m² before and after vitamin D3 supplementation
 - f. To compare vitamin D, hepcidin, and ferritin level in children with CKD and GFR more than 90 ml/min/1,73 m² before and after vitamin D3 supplementation
 - g. To compare vitamin D, hepcidin, and ferritin level between children with GFR less than 90 ml/min/1,73 m² and children with GFR more than 90 ml/min/1,73 m² before vitamin D3 supplementation
 - h. To compare vitamin D, hepcidin, and ferritin level between children with GFR less than 90 ml/min/1,73 m² and children with GFR more than 90 ml/min/1,73 m² after vitamin D3 supplementation

Hypothesis:

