1. Serum hepcidin level is lower after vitamin D3 supplementation in children with CKD
2. Serum ferritin level is lower after vitamin D3 supplementation in children with CKD
3. Serum hepcidin level is lower in pediatric CKD patients with GFR more than 90 ml/min/1,73 m² compare to GFR less than 90 ml/min/1,73 m²
4. Serum ferritin level is lower in pediatric CKD patients with GFR more than 90 ml/min/1,73 m² compare to GFR less than 90 ml/min/1,73 m²

Study Design:

Interventional study

Study Population:

Number of samples:

43 subjects

Inclusion criteria:

- Patients aged 2 to 18 years diagnosed with chronic kidney diseases at [name] hospital
- Parents have signed their child's consent to participate in the study

Exclusion criteria:

- History of blood transfusion 3 months prior
- Liver dysfunction
- Sepsis
- Routine consumption of Vitamin D
- Routine consumption of iron supplement
- Patients diagnosed with iron deficiency anemia

Product Description:

Vitamin D3 with the dose of 2,000 IU

Outcomes:

The primary outcomes being measured in this study are serum vitamin D levels, serum hepcidin levels and serum ferritin levels. These outcomes will be measured in children with CKD before and after 6 weeks of vitamin D3 supplementation. We plan to compare these levels in two groups of CKD patients - those with glomerular filtration rate (GFR) <90 mL/min/1.73 m² and those with GFR ≥ 90 mL/min/1.73 m². Measurement will be done by collecting 3 ml of blood to measure the level of vitamin D, hepcidin and serum ferritin.

Statistical analysis will utilize unpaired T test or Mann-Whitney test will be used to compare vitamin D, hepcidin and ferritin serum level in subjects according to the distribution of the data. Paired T Test or McNemar test will also be used to compare proportion of individually matched event for the two groups before and after vitamin D3 supplementation. Lastly, Pearson or Spearman test will be done to assess the correlation between vitamin D level and hepcidin and ferritin serum level.

Conduct of Trial:

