This study will be conducted as a clinical trial involving children with chronic kidney disease (CKD). Participants will be divided into two groups based on their glomerular filtration rate (GFR): those with GFR <90 mL/min/1.73 m² and those with GFR ≥ 90 mL/min/1.73 m². All participants will undergo initial blood tests to measure serum levels of vitamin D, hepcidin, and ferritin. Following these baseline measurements, the children will receive vitamin D3 supplementation for a specified period. After the supplementation period, blood tests will be repeated to measure the same parameters. We will then compare the pre- and post-supplementation levels of vitamin D, hepcidin, and ferritin within each GFR group, as well as between the two GFR groups. This approach will allow us to assess the effect of vitamin D3 supplementation on serum hepcidin and ferritin levels in children with CKD, and to determine if the effect differs based on the severity of kidney dysfunction as indicated by GFR.

[figure not shown]

Figure 1. Study Procedure

Statistical Aspects and Considerations:

This study employs a comprehensive statistical approach to analyze the effect of vitamin D3 supplementation on serum hepcidin and ferritin levels in children with chronic kidney disease (CKD). We will utilize both descriptive and inferential statistics to examine their data. Descriptive statistics will be used to summarize the categorical data as counts and ratios, while quantitative

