data will be presented as mean values with standard deviation. For inferential statistics, the study will employ Pearson's correlation test to differentiate between groups and assess statistical significance. The significance level is set at $P < 0.05$ for statistical significance and $P < 0.01$ for high significance. The statistical analysis will be conducted using SPSS version 20.0. Important considerations for this study include ensuring an adequate sample size to detect clinically meaningful differences, which will be determined through a sample size calculation. We will account for potential confounding variables, assess whether assumptions are met for the planned statistical tests, handle any missing data appropriately, and conduct sensitivity analyses to evaluate the robustness of results. By addressing these statistical aspects and considerations, our study aims to produce valid and reliable results regarding the effects of vitamin D3 supplementation on serum hepcidin and ferritin levels in children with CKD, comparing outcomes between groups with different glomerular filtration rates ($\text{GFR} < 90 \text{ mL/min/1.73 m}^2$ and $\text{GFR} \geq 90 \text{ mL/min/1.73 m}^2$).

References

Altemose, K. E., Kumar, J., Portale, A. A., Warady, B. A., Furth, S. L., Fadrowski, J. J., & Atkinson, M. A. (2018). Vitamin D insufficiency, hemoglobin, and anemia in children with chronic kidney disease. *Pediatric Nephrology*, 33(11), 2131–2136. <https://doi.org/10.1007/s00467-018-4020-5>

Avner, E. D., Harmon, W. E., Niaudet, P., Yoshikawa, N., Emma, F., & Goldstein, S. L. (Eds.). (2016a). *Pediatric Nephrology*. Springer Berlin Heidelberg. <https://doi.org/10.1007/978-3-662-43596-0>

Avner, E. D., Harmon, W. E., Niaudet, P., Yoshikawa, N., Emma, F., & Goldstein, S. L. (Eds.). (2016b). *Pediatric Nephrology*. Springer Berlin Heidelberg. <https://doi.org/10.1007/978-3-662-43596-0>

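### The planned correlation of vitamin D with hepcidin and ferritin names no GFR adjustment, stratum or visit, so if the children are pooled it may partly reflect kidney function

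*Protocol*

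**What the plan says.** The correlation is the last test named in the Outcomes section: "Pearson or Spearman test will be done to assess the correlation between vitamin D level and hepcidin and ferritin serum level". The sentence does not say whether all children are analysed together or by GFR group, at which of the two visits, or with any adjustment.

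The groups come from the Conduct of Trial section: "Participants will be divided into two groups based on their glomerular filtration rate (GFR"), with the cut at 90 mL/min/1.73 m². That section calls for comparisons inside each GFR group and across the two groups for the before and after levels. It does not mention the correlation.

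The Hypothesis section expects both iron markers to differ by group. Hypothesis 3 reads: "Serum hepcidin level is lower in pediatric CKD patients with GFR more than 90 ml/min/1,73 m² compare to GFR less than 90 ml/min/1,73 m²". Hypothesis 4 reads: "Serum ferritin level is lower in pediatric CKD patients with GFR more than 90 ml/min/1,73 m² compare to GFR less than 90 ml/min/1,73 m²". No hypothesis concerns a vitamin D difference between the groups. Secondary objectives g and h compare vitamin D between them, and the Introduction links deficiency to CKD in general: "Vitamin D deficiency is another critical issue associated with CKD, particularly in children".

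Statistical Aspects and Considerations promises in general terms to deal with confounding, without naming a variable or a method. It also gives Pearson's correlation the task of telling groups apart, which does not settle how the vitamin D correlation is to be run.

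**The concern.** When two groups differ in their means on both variables, pooling them produces a correlation even if the variables are unrelated within each group. The protocol's own hypotheses supply one of the two gaps needed: higher hepcidin and ferritin with GFR below 90. If vitamin D were also lower in that group, the pooled correlation would be pushed below zero. That is the direction the Introduction describes when it ties deficiency to raised hepcidin.

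At stake is how a supporting result is read. A significant negative correlation could be taken as a link between vitamin D and the iron markers when it came wholly or partly from the difference in kidney function.

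**Working it through.** **Stated figure.** There is none to reproduce. The protocol gives 43 children ("It is a clinical trial involving 43 chronic kidney disease patients") with no effect size, SD, expected correlation or group split.

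**Inputs from the protocol.** N = 43. Test level: "The significance level is set at $P < 0.05$ for statistical significance and $P < 0.01$ for high significance". Sidedness is not stated; two-sided 5% is assumed.

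**Assumptions.** Correlation within each GFR group is zero. The groups differ by dx SDs on vitamin D and dy SDs on hepcidin (or ferritin), in opposite directions. The share p of children in one group is set at 21/43 (near-even) or 9/43 (uneven).

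**Critical value.** With 41 df, t = 2.0195, so |r| must exceed 2.0195 / √(41 + 2.0195²) = 0.301.

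**Pooled correlation.** With q = p(1 − p),

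r = −q·dx·dy / √[(1 + q·dx²)(1 + q·dy²)].

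For 21/22, q = (21/43)(22/43) = 0.2499.

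- dx = dy = 0.5: r = −0.0625 / 1.0625 = −0.06
- dx = dy = 0.8: r = −0.1599 / 1.1599 = −0.14
- dx = dy = 1.0: r = −0.2499 / 1.2499 = −0.20
- dx = 0, any dy: r = 0

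For 9/34, q = (9/43)(34/43) = 0.1655. At 1.0 SD, r = −0.1655 / 1.1655 = −0.14.

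**Rejection rates.** 20,000 simulated trials per row, normal data, two-sided 5%. Pooled Pearson is compared with Pearson after removing each group's mean, which is the partial correlation given GFR group, on N − 3 = 40 df.

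| Split | Vitamin D gap (SD) | Hepcidin or ferritin gap (SD) | Pooled r | Pooled rejects | Adjusted rejects |
|---|---|---|---|---|---|
| 21/22 | 0 | 0.8 | 0 | 4.8% | 4.9% |
| 21/22 | 0 | 1.5 | 0 | 5.1% | 4.9% |
| 21/22 | 0.5 | 0.5 | −0.06 | 6.8% | 5.2% |
| 21/22 | 0.5 | 0.8 | −0.09 | 8.8% | 5.0% |
| 21/22 | 0.8 | 0.8 | −0.14 | 14.1% | 4.7% |
| 21/22 | 1.0 | 1.0 | −0.20 | 25.5% | 4.8% |
| 9/34 | 0.5 | 0.5 | −0.04 | 5.6% | 4.9% |
| 9/34 | 0.8 | 0.8 | −0.10 | 9.2% | 5.0% |
| 9/34 | 1.0 | 1.0 | −0.14 | 14.5% | 4.9% |

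Simulation error is about √(0.05 × 0.95 / 20,000) = 0.15 percentage points near 5%, and √(0.25 × 0.75 / 20,000) = 0.3 points near 25%. Spearman was not simulated.

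**Price of the alternatives.** Adjusting for group costs one degree of freedom: with 40 df, t = 2.021 and the critical |r| is 2.021 / √(40 + 2.021²) = 0.304, against 0.301. A separate correlation in a group of 21 has 19 df, t = 2.093, and a critical |r| of 2.093 / √(19 + 2.093²) = 0.433.

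**The case against.** The strongest reply is that the protocol does not specify a faulty analysis; it is silent. Pooling is nowhere stated, and the surrounding text is about two GFR groups. The distortion also needs a vitamin D gap at the 90 cut-off, which no hypothesis asserts: planning to compare vitamin D is not the same as expecting a difference, and every participant has CKD. The protocol promises to handle confounding, and the detail could sit in an analysis plan that is not shown. The correlation serves no listed objective.

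Most of this stands, and it makes the point conditional and minor. It does not remove it. The protocol names the test, and as named it is unadjusted, although the protocol's own hypotheses make GFR group a predictor of both iron markers. The promise on confounding names neither a variable nor a method.

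Three stronger readings are tempting and are not supported:

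- A reader might infer that the groups are known to differ on all three markers. The protocol only hypothesises this for hepcidin and ferritin.
- A reader might infer that both visits would be stacked as 86 independent rows, which would inflate the error further. The protocol proposes no such thing.
- A reader might conclude that correlating levels is wrong and that only changes should be correlated. That is a different question, and the choice between them is a trade-off.

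It is also fair to say that a two-level GFR group removes only the between-group part. Kidney function still varies among children below 90, so some confounding could remain after adjustment.

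**Conclusion.** The point holds in conditional form. The correlation is left unadjusted and fixes neither the population nor the visit. If it is pooled and vitamin D also differs by GFR group, it can show an association that comes from kidney function.

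How far depends on gaps that the protocol does not give. With no vitamin D gap there is no distortion, however large the hepcidin gap. At 0.5 SD on both variables it is slight. It becomes material from about 0.8 SD on both with a near-even split, and is smaller when the split is uneven. These figures assume zero correlation within groups, opposite gaps and normal data.

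Nothing here touches the comparison of levels before and after supplementation, which carries the primary objective.

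**What to change.** In the Outcomes section, replace the simple correlation with a partial correlation (or its rank version) of vitamin D with hepcidin and with ferritin, adjusted for GFR group. Alternatively, report the correlation separately within each GFR group. In either case analyse one visit at a time and show baseline and post-supplementation results separately. Bring the sentence on Pearson's correlation in Statistical Aspects and Considerations into line with this.

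The correlation of within-child changes may be added as a supportive analysis; it need not replace the correlation of levels.

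The cost is wording only. GFR group and both sets of measurements are already part of the study. The adjusted version loses one degree of freedom. The within-group version is less precise because each group is smaller, so the adjusted version is the better choice if only one is reported.

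### With every child on the same vitamin D3 and groups formed only by GFR, the trial can measure change during supplementation, not the effect of vitamin D3 that its primary objective claims

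*Protocol*

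**What the plan says.** The Summary of the Protocol describes two groups of children, above and below a GFR of 90 mL/min/1.73 m², and states: "Both group will be given the same dose of Vitamin D". Conduct of Trial confirms that groups are formed by GFR and that the children are supplemented after the baseline blood test. The planned comparisons are of vitamin D, hepcidin and ferritin before and after supplementation "within each GFR group, as well as between the two GFR groups". No untreated, placebo, delayed-start or historical comparator is described, and Study Design says only that the study is interventional.

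The claims attached to this design are causal:

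- Primary objective: "To assess the effect of Vitamin D supplementation on hepcidin and ferritin serum level in children with CKD".
- Conduct of Trial, first clause: "This approach will allow us to assess the effect of vitamin D3 supplementation on serum hepcidin and ferritin levels in children with CKD".
- Conduct of Trial, second clause: "to determine if the effect differs based on the severity of kidney dysfunction as indicated by GFR".
- Statistical Aspects and Considerations: the opening says that the analysis addresses the effect of vitamin D3, and the closing promises valid and reliable results about its effects.

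Other parts are worded differently. Hypotheses 1 and 2 and secondary objectives e and f speak of levels before and after supplementation. Secondary objectives g and h and hypotheses 3 and 4 compare levels between the GFR groups. The protocol states no limitation about attribution.

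**The concern.** The Conduct sentence is more than loose usage. It states what the approach will allow the investigators to conclude, and an uncontrolled before-after comparison does not allow it. If hepcidin or ferritin falls over the 6 weeks for reasons unrelated to vitamin D (a time trend, regression to the mean, a change in inflammation or co-treatment), the fall would answer the primary objective as though vitamin D had caused it. Likewise, a difference between the GFR groups could be read as a difference in vitamin D effect. At stake is the trial's central conclusion; the data themselves remain usable.

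**Working it through.** **1. What each comparison estimates.** Write τ for the mean vitamin D effect in a GFR group and δ for the mean change over 6 weeks that would have occurred without supplementation.

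- Before-after within a group: mean change = τ + δ. Every child is treated, so no data inform δ separately and τ cannot be isolated.
- Difference in change between GFR groups: (τ₁ − τ₂) + (δ₁ − δ₂). This equals a difference in vitamin D effect only if δ₁ = δ₂, which the design cannot check.
- Difference in post-supplementation levels (objective h): baseline difference + difference in change. Hypotheses 3 and 4 expect lower levels with higher GFR. A post-level difference can therefore arise even when both groups change equally, so comparing levels does not answer the second Conduct clause.

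**2. Whether another part of the protocol supplies the missing element.** Statistical Aspects promises to account for confounding variables. Adjustment among children who are all treated does not recover a shared untreated course. Outcomes plans a correlation of vitamin D with hepcidin and ferritin. As written it correlates levels, and that is association.

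**3. Illustration of size.** The protocol gives no figure to reproduce here.

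Inputs from the Protocol: 43 children (Study Population) and P<0.05 (Statistical Aspects). Assumptions: two-sided paired t test, normal change scores, no vitamin D effect (τ = 0), a shared fall of d SDs of the change score with d = 0.2, 0.3 or 0.5, and a GFR group of 21 (the split is not stated).

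Formula: under drift d, the t statistic is non-central t with n − 1 degrees of freedom and noncentrality d√n. The probability of P<0.05 is the probability that |t| exceeds the 0.975 quantile of the central t.

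| n | critical t | d | d√n | Pr(P<0.05) |
|---|---|---|---|---|
| 43 | 2.018 | 0 | 0 | 0.050 |
| 43 | 2.018 | 0.2 | 1.311 | 0.249 |
| 43 | 2.018 | 0.3 | 1.967 | 0.485 |
| 43 | 2.018 | 0.5 | 3.279 | 0.893 |
| 21 | 2.086 | 0.2 | 0.917 | 0.141 |
| 21 | 2.086 | 0.3 | 1.375 | 0.258 |
| 21 | 2.086 | 0.5 | 2.291 | 0.587 |

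Counting only falls, the direction of hypotheses 1 and 2, the n = 21 figures are 0.139, 0.258 and 0.587. For group sizes from 15 to 28 the falls-only ranges are 0.108–0.174, 0.190–0.334 and 0.438–0.723. The n = 43 rows match the primary objective, which covers all children. The n = 21 rows match the within-group comparison that Conduct of Trial names.

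**The case against.** A single-arm before-after study is a legitimate choice, and the protocol already words hypotheses 1 and 2 and objectives e and f as before versus after. On that view only loose wording is left. This stands in part: the design and those hypotheses and objectives need no change. But the loose wording sits in the primary objective and in an explicit statement of what the design can show.

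The entry criteria also exclude recent transfusion, sepsis, liver dysfunction, routine iron or vitamin D, and diagnosed iron deficiency anaemia. These narrow some competing explanations. They do not remove regression to the mean or changes during follow-up. Adjustment for measured changes, perhaps specified in an SAP that is not at hand, could remove part of the non-drug change under assumptions. No analysis plan can create an untreated course.

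The percentages are generic properties of a paired test. Drift size, drift direction and group split are all assumed, and nothing in the protocol shows that such drift is likely here. That is correct, and the point does not depend on them.

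A reader might also infer that the title, Summary and Introduction must be rewritten. The title is descriptive, the Introduction gives a rationale ("research is warranted to explore the effects of vitamin D supplementation on serum hepcidin and ferritin levels"), and the Summary states an aim. None of them says what this design can establish, so a stated limitation is enough for them.

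**Conclusion.** The point holds. The primary objective, both clauses of the Conduct sentence, and the opening and closing claims of Statistical Aspects attribute to the design a property that it lacks. This follows from the protocol's text alone and needs no numerical assumption. The illustration, roughly 25% to 89% for all 43 children over the assumed drifts, shows only how readily a non-drug change could be called significant.

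Three stronger readings are tempting and not supported:

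- That the trial is invalid or must add a control group. It can validly describe change during supplementation.
- That the paired test has an inflated error rate. With no drift it rejects in 5% of trials; with drift it correctly detects a real change that vitamin D did not cause.
- That rewording alone is enough. A claim about whether change differs by GFR needs a comparison of change, and the listed objectives and hypotheses name only comparisons of levels between groups.

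**What to change.** - Reword the primary objective, the first Conduct clause, and the opening and closing statements of Statistical Aspects to 'change in hepcidin and ferritin over 6 weeks of vitamin D3 supplementation'.
- Reword the second Conduct clause to 'whether the change differs by GFR group'. Add one between-group comparison of each child's change, for example the post-supplementation value adjusted for baseline, or change scores. If the SAP already contains one, refer to it.
- State as a limitation that without an untreated group the change cannot be attributed to vitamin D3. Add that a difference in change by GFR group is not a difference in vitamin D effect unless non-drug change is equal in both groups.
- Leave hypotheses 1 and 2, objectives e and f, the title, the Summary and the Introduction as they are.

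The cost is wording in five statements, the limitation text and one extra analysis of measurements already planned. No child, visit or blood sample is added. The downside is a more modest claim.

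### The protocol promises to show whether the vitamin D3 effect differs by GFR, but no planned comparison sets the before-after change of one GFR group against the other

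*Protocol*

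**What the plan says.** Conduct of Trial describes one course of vitamin D3 for all children, with blood tests before and after, and says the investigators will "compare the pre- and post-supplementation levels of vitamin D, hepcidin, and ferritin within each GFR group, as well as between the two GFR groups". The next sentence says this approach serves two ends: to assess the effect of supplementation, and "to determine if the effect differs based on the severity of kidney dysfunction as indicated by GFR".

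The comparisons are spelled out elsewhere in the protocol:

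- **Objectives of Trial, secondary e and f:** before against after, separately in each GFR group.
- **Secondary g and h:** one GFR group against the other, once at baseline (g) and once at the end. Objective h sets the low-GFR children against "children with GFR more than 90 ml/min/1,73 m² after vitamin D3 supplementation".
- **Hypothesis 3:** "Serum hepcidin level is lower in pediatric CKD patients with GFR more than 90 ml/min/1,73 m²" than in those below 90. Hypothesis 4 says the same of ferritin. Neither names a time point, and neither speaks of change.
- **Outcomes:** "unpaired T test or Mann-Whitney test will be used to compare vitamin D, hepcidin and ferritin serum level in subjects", a paired t or McNemar test for before against after, and a correlation of vitamin D with the two markers.
- **Statistical Aspects and Considerations:** "the study will employ Pearson's correlation test to differentiate between groups and assess statistical significance".

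**The concern.** Whether an effect differs between two groups is answered by one contrast: the mean change in one group minus the mean change in the other. The plan names the parts of that contrast but never the contrast itself. A reader following the protocol would have two indirect routes to the promised conclusion, and neither is a test of it:

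- putting the two within-group p-values side by side, which confuses a difference in significance with a difference in effect;
- comparing the groups at the end, or noting that the groups differ at one time point and not at the other, which lets a baseline gap pass for an effect.

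The second route is a particular risk here. Nothing balances the groups at baseline, because GFR itself defines them, and hypotheses 3 and 4 expect one group to have lower hepcidin and ferritin. The trial could report a GFR-dependent effect that does not exist, or miss one that does.

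**Working it through.** **1. What each planned comparison estimates.** Let the mean levels be A0 and A1 (before and after) in one GFR group, and B0 and B1 in the other. The question is about D = (A1 − A0) − (B1 − B0).

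| Planned item | Estimates | Is it D? |
|---|---|---|
| Objective e | A1 − A0 | No |
| Objective f | B1 − B0 | No |
| Objective g | A0 − B0 | No |
| Objective h | A1 − B1 = (A0 − B0) + D | Only if there is no baseline gap |
| Vitamin D–marker correlation | Association of levels | No |
| Pearson's test between groups | With group coded 0/1, the unpaired t-test of whatever variable is entered; no change variable is named | No |

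This table settles the point. The figures below only show how far the indirect routes can mislead.

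**2. Inputs.** From the protocol: 43 children in all and significance at 0.05. Assumed, because the protocol does not give them: two-sided tests, normal data, equal SD before and after, pre-post correlation 0.5 to 0.7, group splits of 21/22, 13/30 or 10/33, and the gaps and changes stated below. The protocol has no figure of its own on this point to reproduce.

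**3. After-only comparison when the true change is identical (D = 0).** The non-centrality is g × √(n1·n2/(n1+n2)), where g is the baseline gap in SD of level. For 21/22, √(21×22/43) = 3.278, and the critical t on 41 df is 2.02.

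- g = 0.3: 0.98, rejection 16%
- g = 0.5: 1.64, rejection 36%
- g = 0.8: 2.62, rejection 73%

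**4. Objectives g and h read together, D = 0.** Simulation with 40,000 runs per cell; probability that exactly one of the two tests is significant, 21/22 split:

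| Gap (SD of level) | Correlation 0.5 | Correlation 0.7 |
|---|---|---|
| 0 | 8% | 7% |
| 0.3 | 20% | 15% |
| 0.5 | 31% | 24% |
| 0.8 | 28% | 22% |

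Over all three splits, the range at gaps of 0.5 to 0.8 is 21 to 33%. The unpaired test on change rejects in 5% throughout.

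**5. Side-by-side paired tests, equal true change.** With pa and pb the power of each paired t-test, the chance that exactly one is significant is pa(1 − pb) + pb(1 − pa). For 21/22 and a change of 0.5 SD of change: 0.587 × 0.391 + 0.609 × 0.413 = 0.48.

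| Split | Range over changes of 0.3 to 0.8 SD of change | At 1.0 SD |
|---|---|---|
| 21/22 | 11–49% | 1% |
| 13/30 | 25–56% | 9% |
| 10/33 | 39–62% | 20% |

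**6. A real difference missed.** Take true changes of −1.2 and −0.4 SD of level (D = 0.8 in size), 21/22 split. Both paired tests are significant, so no difference shows, in 43 to 64%. With a 0.5 SD baseline gap, the before and after tests agree in 49 to 52% if the higher-baseline group falls more, but in about 37% if the lower-baseline group does; with no gap they agree in 28 to 29%. The test on change detects the difference in 73 to 91%.

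**7. Limit of the remedy.** Non-central t power of the unpaired test on change:

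| Split | Power at 0.5 SD of change | Difference for 80% power |
|---|---|---|
| 21/22 | 36% | 0.88 SD |
| 13/30 | 31% | 0.95 SD |
| 10/33 | 27% | 1.04 SD |

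**The case against.** **Reach.** The effect-by-GFR statement occurs once, in a narrative sentence. It is not among the objectives or hypotheses, and deleting it would settle the matter. This stands, and it limits the weight of the point.

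**A kinder reading.** The comparison between the two GFR groups might mean comparing the pre-post contrast, and the unpaired-test sentence fixes no time point. This does not hold up: the object in both places is levels, and objectives g and h each fix a single time.

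**The SAP may supply it.** The choice between a change score, an interaction term and a baseline-adjusted model is often left to a SAP, and the protocol also promises attention to confounders and sensitivity analyses. That promise names no contrast. The protocol itself asserts that the comparisons it lists will answer the question, and that assertion is wrong whatever an unseen document adds.

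**The percentages presuppose a decision rule.** The protocol nowhere says that a differing effect will be declared when two tests disagree. This is fair: the rates show what happens if the results are read that way and are not properties of the stated plan. They also fall as the common change grows, and the agreement figure in step 6 depends on which group falls more. None of this supplies the missing contrast.

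**Conclusion.** The concern holds and should be fixed. The protocol claims that comparisons of levels will determine whether the effect differs by GFR, and none of its objectives, hypotheses or named tests compares the change between groups. That conclusion rests on the text alone.

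The size is illustrative. Under the assumptions listed, with no true difference in effect, the indirect readings would suggest one in roughly a fifth to nearly three quarters of trials when the baseline gap is 0.5 to 0.8 SD, against 5% for a direct test. With no baseline gap, the two between-group comparisons mislead little (7 to 8% disagreement), but the side-by-side paired tests still can. The fault reaches only the effect-by-GFR statement; the primary objective and hypotheses 1 and 2 stand.

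**What to change.** Either of two changes will do.

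- **Add the contrast.** In Conduct of Trial and Outcomes, state that each child's change (after minus before, on a log scale fixed in advance if the data are skewed) will be compared between the GFR groups with the unpaired t or Mann-Whitney test already named. A group-by-time term would also serve; it is equivalent to the t-test on change. Report the difference in change with a 95% CI and label it exploratory, because power is about 36% at best among the splits considered for a difference of 0.5 SD of change. Add that after-only gaps, disagreement between the before and after tests, and side-by-side within-group p-values will not be used to claim a differing effect. A baseline-adjusted comparison can give a different answer in non-randomised groups, so the choice should be made in advance.
- **Or withdraw the claim.** Delete the clause on a differing effect from Conduct of Trial.

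The cost is protocol wording and one derived variable, or the deletion of one clause. No new data or extra patients are needed.
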